### Participants

Participants will be recruited in the United States. A brief study description will be distributed via lab websites, social media, clinicaltrials.gov, and brochures to local agencies.

Inclusion criteria will consist of (1) Seeking treatment for social anxiety or panic disorder and demonstration of elevated scores (greater than two standard deviations of the normed mean) on standardized scales for anxiety (i.e., Mini SPIN or PDSS), (2) Age 18 to 65, (3) Either stabilized on psychotropic medications (1 month for benzodiazepines and beta blockers, 3 months for heterocyclics and SSRIs; self-reported) or medication-free (self-reported), (4) English-speaking, and (5) Clinical severity rating of 4 or higher on the Structured Clinical Interview for DSM-5 (SCID-5) for either panic disorder or social anxiety.

Exclusion criteria will consist of (1) Patient report of serious medical conditions – such as respiratory (e.g., chronic obstructive pulmonary disease), cardiovascular, pulmonary, neurological, muscular-skeletal diseases – or pregnancy, (2) History of suicidal ideation or self-harm in the past year; history of suicide attempts in the last 10 years, (3) History of bipolar disorder, psychosis, mental retardation or organic brain damage, (4) Substance abuse dependence within last 6 months, (5) Concurrent therapy focused on anxiety

Participants will be allowed to be in other forms of therapy, provided the therapy does not focus on anxiety (e.g., supportive counseling) and they have been stabilized on this alternative therapy for at least 6 months.

Interventions. Both interventions will entail 9 weekly exposure treatment sessions which are 60 minutes each, with the exception of first session which will be 90 minutes. Treatment sessions and laboratory assessments will be conducted at the UCLA Psychology Clinic and at UCLA's Anxiety and Depression Research Center laboratory.

Inhibitory Retrieval Condition (Experimental Comparator)

Participants will receive exposure therapy focused on maximizing extinction learning and expectancy violation. Participants will complete an OptEx Nexus to identify conditional stimuli (CS), unconditional stimuli (US), safety signals, and occasion setters. Exposures will be designed to “test out” if the US will occur. Consistent with associative learning principals, participants will conduct repeated exposure to the principal conditional stimulus (along with additional exposure to other CSs).

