This condition includes techniques that incorporate associative learning principles such as deepened extinction, increasing attentional salience of the CS, variability in contexts and stimuli, occasional reinforcement, and mental reinstatement of extinction learning. Our manual is available to clinical researchers upon request.

Habituation Treatment (Active Comparator)

Participants will receive exposure therapy aimed at maximizing habituation and reducing fear responding. This condition includes techniques derived from the extant literature on habituation and dominant habituation models of exposure therapy. These include, but are not limited to, maintaining the exposure until fear declines, maintaining similarity across exposures, repetition of exposures until between session fear has declined, and a gradual approach to feared stimuli using an exposure hierarchy.

A list of feared situations will be generated and ranked in ascending order on the level of expected distress in that given situation (fear hierarchy). Treatment will begin with exposure to a moderately distressing stimulus (e.g., subjective units of distress or SUDS of 50-60) and continue through the individual's fear hierarchy towards the highest rated distressing situation. A given exposure will be focused on the given item on the fear hierarchy until initial SUDS has decreased by 50% or 45 minutes has passed. For example, if an individual reports that having a conversation with a stranger would elicit a distress rating of 80 out of 100, the individual would continue their exposure to this situation until they reach a distress rating of 40 or 45 minutes had passed. The same in-session exposure will be repeated between-session (consistent with models of habituation). Individuals will move up their fear hierarchy once between-session habituation (50% reduction in SUDS from the first exposure to this stimulus) has been achieved. Our manual is available to clinical researchers upon request.

Therapist Training, Supervision, and Fidelity

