### **Principal Outcome Measures.**

Self-reported symptom severity of social anxiety and panic disorder at pre-treatment, mid-treatment, post-treatment, and follow-up. Self-reported symptom severity of social anxiety disorder and panic disorder will be assessed using the Liebowitz Social Anxiety Scale-Self Report (LSAS; Baker et al., 2002) and Panic Disorder Severity Scale-Self Report (PDSS-SR; Houck et al., 2002), respectively.

The LSAS is a 24-item measure of social anxiety symptoms during the past week. The measure assesses the severity (0 = none, 3 = severe) and frequency (0 = never, 3 = usually) of social anxiety and social avoidance, with total sum scores ranging from 0 to 144. Higher scores indicate greater symptom severity and frequency. The LSAS demonstrates excellent internal consistency and correlational data corroborate its convergent validity (Baker et al., 2002).

The PDSS-SR is a self-report instrument adapted from the interviewer-administered Panic Disorder Severity Scale which assesses panic disorder symptom severity. This self-report measure assesses panic-related anxiety, distress, and avoidance in the past week.

Clinician-rated severity of social anxiety or panic disorder. Clinician severity rating (0-8) of social anxiety or panic disorder will be assessed using the Structured Clinical Interview for DSM-5 (SCID-5). The SCID is a semi-structured diagnostic interview, which will be completed by trained graduate students and reliability-checked by [name] or [name]. This interview (1) diagnoses anxiety disorders, mood disorders, somatoform disorders, and substance disorders; and (2) screens for psychosis. The results of the diagnostic evaluation will be presented at weekly meetings with the [name] or [name], who will check the diagnostic judgment and eligibility of the subject. Potential participants must receive a clinical severity rating of four or higher for their social anxiety or panic disorder in order to be eligible.

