### Randomization and Masking

The research coordinator will enroll participants and assign them to interventions. Participants will be randomized 1:1 to either habituation or inhibition-based exposure therapy via centralized, computer-generated allocation sequences. Because of the nature of the study, only outcome assessors will be masked to group allocation.

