### Statistical Methods

In order to examine the principal outcomes, we will use multilevel modeling Stata 17.0 to test a Condition x Time interaction in predicting normalized symptom scores. We will use repeated measures as a Level 1 factor and Condition as a Level 2 factor. Condition will be included as a categorical variable (Inhibitory, Habituation). For the principal analyses (LSAS and PDSS at pre-treatment, mid-treatment, post-treatment, and follow-up), Time will be included as a continuous variable. We will then follow-up with models using Time as a categorical variable involving three time-points (mid-treatment, post-treatment, 3-month follow-up) to examine differences at specific time points (post-treatment and follow-up) while simultaneously examining potential differences in the slopes of

the inhibitory retrieval and habituation condition from mid-treatment to post-treatment and post-treatment to follow-up. Similar models will be run for secondary outcomes (e.g., weekly Mini-SPIN, weekly PDSS, and BAT). Pre-treatment normalized symptom scores will be included as a covariate. As we conducted exposure therapy both in-person and remotely (due to COVID-19), we will also include Remote Therapy as a categorical factor (in-person, remote) in the models.

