### Safety Monitoring

Study staff will be available 24 hours to respond to urgent issues. All staff will be able to provide information about local emergency facilities. The therapist will generally be the first person to respond to a participant with a problem. They will handle some events immediately. If they are not able to manage the emergency event, they will contact the PIs, who will also be available 24 hours by cell phone to assist with participant management or crisis intervention.

Monitoring and reporting of all adverse events. The following adverse events will be monitored: suicide attempts, study dropout, psychiatric hospitalizations, and clinical deterioration, defined as emergent suicidal ideation or suicidal plan, or emergence of a new psychiatric or medical diagnosis or behavior posing significant risk to the subjects or others.

The following grading system will be used to assess the seriousness of any adverse events:

0 No adverse event or within normal limits

1 Mild adverse event

2 Moderate adverse event

3 Severe adverse event resulting in hospitalization or a persistent or significant disability/incapacity

4 Life-threatening or disabling adverse event

5 Fatal adverse event

Study research staff will be trained in what events to look for and to report any such events to Drs. [name]. If the event is graded 2-4, Drs. [name] will interview the Ps and take the appropriate action. Drs. [name] can be reached promptly by telephone. UCLA's IRB will be notified within 24 hours of any serious adverse events (SAEs), in the 3-5 range. Within a week of any SAEs, [name] will determine whether the adverse event affects the Risk/Benefit ratio of the study and whether modifications to the protocol (at Risks to Subjects) or consent form (at Risks and Inconveniences) are required. [name] or the IRB has the authority to stop or modify the study.

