[name] will conduct a review of all non-serious adverse events at least quarterly. They will evaluate the types, frequency, and severity of the adverse events and determine if modifications to the protocol or consent form are required. If an event qualifies as a serious adverse event, then the serious adverse event will be reported to IRB. A summary of the nonserious adverse events will be reported to the IRB at minimum, when yearly re-approval of the IRB protocol is sought. The summary will include number of Ps enrolled, treatment retention and reasons for drop-out, and a synopsis of graded adverse events to date. [name] or the IRB has the authority to stop or modify the study.

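### Worsening of the treated panic disorder or social anxiety is not listed as clinical deterioration, and no count of patients who worsened is planned

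*Combined protocol and SAP*

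**What the plan says.** Safety Monitoring names four kinds of event to watch for. Three are attempted suicide, leaving the study and psychiatric admission. The fourth is "clinical deterioration, defined as emergent suicidal ideation or suicidal plan, or emergence of a new psychiatric or medical diagnosis or behavior posing significant risk"; the risk may concern the participant or other people. The section adds a 0 to 5 grading scale, a review of non-serious events at least quarterly, and a yearly summary to the IRB covering enrolment, "treatment retention and reasons for drop-out, and a synopsis of graded adverse events to date".

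The inclusion criteria under Participants require a "Clinical severity rating of 4 or higher on the Structured Clinical Interview for DSM-5 (SCID-5) for either panic disorder or social anxiety", so the treated disorder is present before randomisation.

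Scores that could show worsening are collected. Under Principal Outcome Measures, "Clinician severity rating (0-8) of social anxiety or panic disorder will be assessed", and Table 1 places that rating at weeks 0, 10 and 24. Table 1 schedules LSAS-SR and PDSS-SR at pre-treatment, mid-treatment, post-treatment and follow-up. PDSS-SR and Mini-SPIN are also given weekly. On masking, "only outcome assessors will be masked to group allocation".

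Statistical Methods uses the symptom scores to "test a Condition x Time interaction in predicting normalized symptom scores", with follow-up models at specific time points. It sets no threshold for individual worsening.

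**The concern.** Deterioration is defined by suicidality, a new diagnosis or risk behaviour. A participant whose existing disorder becomes more severe, with none of these, falls outside it. If that participant also stays in the study and is not admitted to hospital, none of the four listed events applies.

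The analysis does not recover the case. A Condition x Time model describes how average scores move in each arm. It does not say how many individuals ended above their starting point, and a good average can coexist with a few clear deteriorations.

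What is at stake is the account of harm. Both arms receive active exposure therapy, and the two models handle fear differently: one holds the exposure until distress falls or a time limit is reached, while the other includes "occasional reinforcement, and mental reinstatement of extinction learning". A reader choosing between them would want the number who got worse beside the average benefit.

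**Working it through.** **Reading the sections together.** Take a participant who enters with a clinician rating of 5 and leaves treatment at 7, with no suicidality, new diagnosis, risk behaviour, admission or dropout.

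- Definition of deterioration (Safety Monitoring): not met, because the disorder was present at entry.
- Other three listed events: not met.
- Yearly IRB summary: counted as enrolled and retained, but not shown as worse on this ground.
- Statistical Methods: contributes to the arm's average only.
- Protocol Amendments: no entry changes the definition or adds a count.

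The conclusion rests on this reading and needs no arithmetic.

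**How many such patients there might be.** The plan gives no figure to reproduce, so this is a range under assumptions.

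Inputs:
- Reliability r of the symptom scale: .80, .90, .95 (assumed; the documents give no value).
- Mean improvement m: 1.0 baseline SD (assumed).
- Pre-post correlation c: .3, .5, .7 (assumed). The .5 is the Sample Size section's input for a two-measure ANOVA, not an estimate for these scales, so it is varied.
- Equal variances before and after, and normally distributed change (assumed).
- Completers: 62 (Sample Size), so 62/2 = 31 per arm.

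Formulas, in baseline SD units:
- Reliable-change threshold T = 1.96 × √(2(1 − r)), giving 1.240, 0.877 and 0.620 for r = .80, .90 and .95.
- SD of change S = √(2(1 − c)), giving 1.183, 1.000 and 0.775 for c = .3, .5 and .7.
- Proportion worsening reliably = 1 − Φ((T + m)/S).

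Results at m = 1.0:

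| c | r = .80 | r = .90 | r = .95 |
|---|---|---|---|
| .3 | 2.9% | 5.6% | 8.6% |
| .5 | 1.3% | 3.0% | 5.3% |
| .7 | 0.2% | 0.8% | 1.8% |

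For example, at c = .3 and r = .95: (0.620 + 1.0)/1.183 = 1.369, and 1 − Φ(1.369) = .0855. At c = .7 and r = .80: 2.240/0.775 = 2.89, and 1 − Φ(2.89) = .0019.

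Per arm of 31 completers: 31 × .0019 = 0.06 to 31 × .0855 = 2.65, or roughly 0 to 3. If attrition is instead exactly 25% of 90, 67.5 remain, or 33.75 per arm, and the upper end is 33.75 × .0855 = 2.9, which changes nothing.

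The result also depends on the assumed improvement. At c = .5, m = 0.5 gives 4.1% to 13.1%, and m = 1.5 gives 0.3% to 1.7%.

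**What a by-arm count could show.** With all 45 per arm (90/2) scored, 2 against 1 is a difference of 2.2 points with a Newcombe 95% interval of −7.7 to 12.8. Zero of 45 has a Wilson upper limit of 1.96²/(45 + 1.96²) = 7.9%. If only 31 have scores, that limit becomes 1.96²/(31 + 1.96²) = 11.0%.

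**The case against.** The strongest reply is that the list need not be exhaustive. It sits under a heading that covers adverse events of every kind, the grading scale has mild and moderate levels, and the quarterly review takes in all non-serious events. Nothing forbids staff from recording worsening of the treated disorder. This stands in part: informal capture is possible. But the plan does not require it and sets no common rule, so recording could differ between therapists or arms.

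A second reply is that clinicians would notice. Therapists have weekly supervision, PDSS-SR and Mini-SPIN are completed before each session, and the therapist is generally the first to respond to a problem. This stands fully. A reader might infer that worsening goes unwatched and that participants are left unprotected; the documents do not support that. What is missing is a rule for counting and reporting.

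A third is that severe worsening often surfaces as dropout, admission or suicidality, all of which are monitored. That is true for some patients, so the figures above are upper figures for what the definition misses. It does not cover those who complete treatment without such an event.

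Finally, temporary distress is expected in exposure therapy. That is a good reason not to count weekly rises, but it does not explain away a score above baseline at week 10 or week 24.

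**Conclusion.** The point holds as a gap in harm reporting. The definition does not list worsening of the treated disorder, nothing elsewhere plans a count, and a completer who is clearly worse in that disorder alone need not appear as a harm.

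Two stronger readings are tempting and unsupported. One is that the efficacy result is distorted: worsened scores enter the planned models like any others. The other is that a substantial number of patients would be missed: the documents give neither scale reliability nor expected improvement, so the range of about 0.2% to 8.6%, or roughly 0 to 3 of 31 completers per arm, rests wholly on the stated assumptions. At such counts a table describes harm but cannot separate the arms.

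The change is a cheap improvement of optional priority.

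**What to change.** In Safety Monitoring, add to clinical deterioration a rise from week 0 beyond a reliable-change threshold, fixed before analysis, on the scale matching each disorder rated 4 or higher at entry: PDSS-SR for panic disorder, LSAS-SR for social anxiety. A participant with both disorders is assessed on both scales. Use weekly rises at most to prompt clinical review, since they may reflect the exposure technique itself.

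In Statistical Methods, add one descriptive table by arm for all randomised participants: the number worsened at week 10 and at week 24, and the number with no score at each. The missing count matters because LSAS-SR is not collected weekly, so a participant with social anxiety who leaves before mid-treatment may have no later score. Give risk differences with 95% confidence intervals and no significance claim. If the masked clinician rating is tabulated as well, use a pre-stated rise of 2 or more points, because a one-point rise can be rating noise.

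Statistical Methods refers to delivery in the past tense ("As we conducted exposure therapy both in-person and remotely"). If treatment is complete, only the by-arm count from stored scores still applies, with the threshold fixed before those data are analysed.

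The cost is one sentence and one table, with no new visits or staff. The downsides are that the threshold needs a reliability value the documents do not give, and that the intervals will be wide.

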### Protocol Amendments

Date	Change
05/05/2016	The Acceptance and Action Questionnaire (AAQ) was removed from the protocol.
05/19/2017	The Fear Inhibition Questionnaire (FIQ) was added to the protocol.
March 2020	COVID Protocol Changes . Due to the COVID-19 outbreak, all study procedures will be adapted to a virtual format, i.e.,

	
 
• All of our therapy sessions will be conducted via a video teleconferencing platform called Zoom.
 
• Access to telehealth resources (for Zoom treatment sessions) has been added to inclusion criteria.
 
• All collection of psychophysiological data collection (e.g., skin conductance, heart rate) has been discontinued as of March 2020.
 
• Behavioral tasks been adapted for remote accessibility.             
 
1. Mobile Generalization of Learning: delivered electronically through the FLARe mobile application. Participants will be asked to download the FLARe application on their mobile device (free of charge, using a unique study ID and password). The first task is designed to measure generalization of acquired fear. It will consist of the following types of stimuli: two CS+, one CS-, and eight generalization stimuli (GS's). All stimuli presented during the fear conditioning paradigm were modeled after Barry et. al, 2014, and consisted of artificial, two-dimensional combinations of abstract shape and color that mimicked the general structure of real-world animals. This task will consist of three phases: acquisition, extinction and retest (retest will occur on day 2). Acquisition will consist of 28 trials: 7 presentations of CS1+, 7 presentations of CS2+ and 14 presentations of the CS-. On CS+ trials, the CS+ stimuli will be paired with the US (i.e., an aversive sound). The US will never be paired with the CS-. The acquisition phase is designed to teach participants to associate the CS+ stimuli with the US such that the CS+ comes to predict the US. The extinction phase will involve 33 trials: 11 presentations of the CS1+, 11 presentations of a novel stimulus (GS+), similar in appearance to that of CS2+, and 11 presentations of the CS-. CS+ trials will not be presented with the US during this phase.
 
2. Virtual Behavioral Avoidance Test (BAT): the BAT has been adapted to a virtual format such that speeches will occur over Zoom.
 
 
 

2021	
Experimental Sampling. Participants will be prompted twice per day, once in the morning and once at night, with Qualtrics links. These links will be sent at 9am and 6pm, and they will expire after 6 hours. Participants will receive these links for five days, beginning the evening of their second and eighth sessions. They will also receive text reminders two hours prior to the expiration date as required.
 
On the first day, they will only receive the evening survey. Thus, they will receive 18 total surveys. In addition, participants will complete a virtual assessment to measure cognitive response to emotional material. This virtual session will last approximately two hours in which participants will engage in several tasks, each separated by a rest interval of five minutes. The lab assessment will be split over two days, separated by approximately one week.

